Study participants will be contacted by a member of the study team each week either by phone or by email to monitor adherence to the intervention and to monitor self-reported health changes. Study team members will fill out a weekly log to ensure that volunteers have been contacted. If any abnormalities are reported, the study physician will be informed. The study physician will advise the participant to follow up with their primary care physician and also decide if the participant can continue with the intervention.

Participants will receive a compliance calendar used to track their supplement intake at visit 2.

Participants will be required to return any unused supplements and compliance calendar at visits 3, 4 and 5. Participants that miss a visit beyond the allowed interval (4 weeks \pm 1 week from previous visit) will be instructed to discontinue their supplement, if they have not done so already, and they will be removed from the study.

V. Location

This study will be performed at the Metabolic Research Unit and Vascular Biology Laboratory at the Jean Mayer USDA Human Nutrition Research Center on Aging at Tufts University, located at [name].

DXA scans will be performed at the Body Composition Analysis Center at Tufts University Friedman School of Nutrition and Science Policy, located at [name].

VI. Transportation

Volunteers will be required to provide their own transportation to the HNRCA. The building is accessible by public transportation. However, if

participants should choose to drive, they can obtain parking validation at a reduced cost.

VII. Personnel who will conduct the study

a. Present During Study Procedures:

Study Nurse
Study Coordinators
Principal Investigator

b. Primary Responsibility for the Following Activities

i. Obtaining Informed Consent

Authorized MRU staff
Principal Investigator
Study Coordinators

ii. Providing On-Going Information to the Study Sponsor and the IRB

Principal Investigator
Co-Investigator
Study Physician

iii. Maintaining Participant's Research Records

Authorized MRU staff
Principal Investigator
Study Coordinators

VIII. Subject Payment

Screening Stipend: \$25

Visit 1 Stipend: \$50

Visit 2 Stipend: \$150

Visit 3 Stipend: \$50

Visit 4 Stipend: \$50

Visit 5 Stipend: \$305

Subjects will only be paid for each completed visit, and will not be paid if they withdraw or are withdrawn from the study.

IX. Confidentiality

The identity of the volunteers, medical records and data relating to this research will be kept confidential, except as required by law and except for inspections by the USDA or the Tufts Medical Center

Institutional Review Board. The medical records will be filed in the medical record room only available to designated research staff. Upon entry into the research study, the volunteer will be assigned a unique code number. For storage, blood and urine samples will be identified with this unique code number (not related to medical record number), date, laboratory generated login number and sample description (i.e. plasma, serum, urine).

All samples and data generated from the research study will be labeled and/or recorded with a unique code number and no other identifier. The information that will allow the unique code number to be linked to the volunteer's name will be stored as a password-protected computer file. Samples will be stored until all analyses are complete. If blood samples collected during the course of this research study are sent outside the HNRCA for analysis, they will be labeled in a manner that contains no information that can make it possible to trace the sample back to the volunteer as an individual. At the conclusion of the study, the information file that would allow linking of the volunteer's identification information with the sample labels will be destroyed. After the research study is completed data and samples will be stored in a manner such that the identity will not be traceable.

Volunteers' records will be filed in the Metabolic Research Unit's Medical Records File Room located on the 11th Floor of the Human Nutrition Research Center. Research records, including volunteer records, will be retained for a period of 7 years after completion of the study.

[name] will have access to the key to identity codes. [name] will have access to the de-identified data. Laboratory personnel responsible for analyzing the samples will have access only to the de-identified data. The study statistician will have access only to the de-identified data.

The study physician and nurses, the PI and Co-I, and Research Coordinators will have access to the research records.

X. Alternatives

Participation in this study is entirely the participant's choice. Participants may withdraw from the study at any time for any reason. Versions of the study supplement are available for purchase from vendors outside of the study.

XI. Payment

All stipends will be mailed to participants in the form of checks 2-3 weeks after they complete each visit. Participants who are removed from the study or choose to drop out will be paid for their completed visits only, and will not be paid if they are removed or choose to drop out before the completion of any study visit. In the event of a government shutdown or any other emergency situation, stipend will be delayed until the shutdown or emergency has ended.

F. Specific Procedures Used Throughout this Study

Distribution and Storage of Dietary Supplement

Supplements and placebo will be labeled in a binary (e.g., A or B) fashion without study staff's knowledge of which is which. Both supplement and placebo will be stored in locked cabinets at the MRU. The two will be distributed to participants, in accordance with their randomization scheme, starting at visit 2. Participants will receive an extra week's worth of supplements at each visit wherein supplement is distributed in anticipation of events that may keep volunteers from attending their next visit after 4 weeks.

Weight and Height:

Body weight will be measured during each visit to the HNRCA, aside from visit 1. Participants will be asked to change into scrubs provided by MRU during weight measurement to ensure the most accurate measurement.

Height will be measured at each visit to the HNRCA except enrollment. Shoes and head dressings or ornaments will be removed. Measurements will be taken according to standard procedure.

Waist and Hip Circumference:

Waist and hip circumference will be measured at visits 2 and 5. Measurements will be taken against the skin. Waist circumference will be measured at the approximate midpoint between the lower margin of the last palpable rib and the top of the iliac crest. Hip circumference will be measured around the widest portion of the buttocks with the tape parallel to the floor. These measures will be performed in duplicate and averaged.

Resting Metabolic Rate (RMR):

RMR measures will be performed only at the visits 2 and 5. Subjects will arrive at the HNRCA in a fasted state. Subjects will undergo bed rest for 30 min prior to measurement. Systolic and diastolic blood pressure will be measured. Measures of VO_2 and VCO_2 will be made

using an indirect calorimeter calibrated using test gases of known concentration. Subjects will be instructed to relax and avoid fidgeting and sleeping during the measurements. Measures will be made under thermo-neutral conditions for 40 minutes. Rates of energy expenditure will be calculated from VO_2 and VCO_2 using Weir's equation. Fasting oral temperature will be measured on days in which RMR is measured.

Dual-Energy X-Ray Absorptiometry (DXA):

DXA measurement will be performed only at the visits 2 and 5. Once subjects have completed measures at the HNRCA, they will be escorted to the Body Composition Analysis Center. The subject should be asked about and examined for metal that could be in the scan path. Typical items to look for are earrings, eyeglasses, wristwatches, coins, rings, buttons, buckles, zippers, and support braces. The subject must remove shoes, and it may be necessary to remove skirts, slacks, brassieres, etc. If clothes are removed, a medical cotton gown will be provided during the scan. Subjects will be asked to lie down on the scan table without allowing their hands and legs to overlap while the scan is performed. The analysis of each whole body scan will generate values for total body lean, total BMC, total body fat, total body mass, trunk fat, trunk lean, total bone mineral density (BMD), lumbar BMD, upper extremity fat, upper extremity lean, lower extremity fat and lower extremity lean. To minimize error, each patient will be scanned on the same machine from baseline to final. Scans will be analyzed by the Body Composition Analysis Lab.

Electrocardiogram (EKG):

An EKG will be performed by MRU staff at visits 2 and 3. Areas of participant's chest, arms and legs will be rubbed with alcohol and 12 electrodes will be attached to the skin. Participants will be required to lie still on their backs in bed while electrical activity is recorded by these electrodes. Electrodes will be removed after the test, which takes approximately 20 minutes to administer.

Skinfold Thickness:

To obtain more specific subcutaneous fat measurements we will perform skinfold thickness tests. Tests will be performed at visit 2 and visit 5. Participants will be asked to remove their shirts in order to obtain the measurements. Skinfold thickness will be measured at four sites: subscapular, suprailliac, the biceps and the triceps. All measures will be performed on the participant's right side unless it is not possible to do so. Sites will be identified through anatomical landmarks and measurements. The skinfold site will be marked. The participants skin will be pinched approximately 1cm above the mark using the thumb and index finger, and simultaneously pulled away from the underlying muscle to form the skinfold. While the pinch is maintained the caliper

jaws will be opened and positioned on the mark approximately 1cm below the thumb and index finger. The caliper jaws will be allowed to close around the skinfold. Two to four seconds after the caliper pressure is released the reading will be taken. This process will be repeated until subsequent measurements are within 1-2mm of each other. The subscapular measure will be taken from the bottom point of the shoulder blade. Suprailiac measure will be taken just above the top of the hip bone. Triceps will be measured at the posterior midline of the upper arm, and biceps at the anterior midline of the upper arm.

Questionnaires:

The following questionnaires will be administered:

Beck Depression Inventory: this questionnaire will be administered by MRU staff at screening and visit 5 to assess volunteer's psychological state. If subjects score ≥ 20 , they will be informed of the result and a recommendation will be made to follow up with their physician.

Three Factor Eating Questionnaire: This questionnaire will be administered by study team staff at visits 2 and 5.

Food Cravings Questionnaire-trait: This questionnaire will be administered by study team staff at visits 2 and 5.

Stanford 7-Day Physical Activity Recall: This questionnaire will be administered by study team staff at visits 2, 3, 4 and 5.

Volunteer Consent and Safety:

The protocol will be reviewed and approved by the Tufts Institutional Review Board (IRB), and written informed consent will be obtained from all participants. Study volunteers will be given the opportunity to read consent forms in a quiet area free of noise and distraction. Consent forms will be thoroughly reviewed with the volunteer and all of their questions will be answered to the volunteer's satisfaction. Comprehension of study information will be assessed by asking volunteers to restate their understanding of presented information in their own words. Participants will be told they can decline participation at any time for any reason. Participant identifiers will be kept in a separate file from data. Data collection forms will not have participant identifiers. The participant's identity and records relating to the prescreening and screening procedures will be kept confidential in locked cabinets at all times at the Volunteer Recruitment Services, and at the MRU, respectively, whether or not the participant qualifies for the study. The information kept may be used to invite the individual to participate in future studies at the HNRCA. If a participant chooses not

to have their contact or other information kept in our records for this or other reasons, the participant need only to contact the Volunteer Recruitment Services Department by telephone or email to make this request, and all of their records will be destroyed. All study records for all participants will be kept confidential, and only the study P.I., Co-P.I., study physician, and study coordinators will have access to participant identifying information, if needed; otherwise, only de-identified data will be transferred to co-investigators. All data will be kept in secure files and locked data cabinets. Identifiers will not be destroyed at any point.

Participants and nursing staff will be able to reach the study physician, [name], or a covering physician 24 hours/day. Specific participant complaints will be addressed on an individual basis and appropriate referrals to primary care providers or other health care providers will be made. Participants' health status will be assessed weekly through phone or email and will be updated by the members of the study team. While there is no evidence to suggest so, there might be some adverse effects from EMIQ's effect on fat loss, or EMIQ itself. If these problems are reported by participants, the condition will be assessed to determine if these adverse events are potentially study-related. Further, in the case of these and any other adverse event, the study physician will advise participants on the appropriate assistance or action to take, and then counseled to seek further appropriate assistance.

Compensation will not be available for any research-related injury, and treatment may incur charges for the subject. The Nursing staff at the MRU is basic BLS (CPR) certified and trained in the use of an automatic external defibrillator (AED). In all emergency situations, the MRU Nursing staff will provide immediate basic life support (BLS) response, call 911 and continue to provide emergency supportive care as needed (e.g., monitoring, oxygen, airway maintenance) until emergency medical service (EMS) arrives. Their philosophy is to provide early access to the most appropriate and advanced care for treatment of study subjects. Treatment by the MRU Nursing staff and/or the staff physician is provided at no cost to the participants. All additional treatment including the cost of an ambulance is charged to the study subject. There are no funds available for these costs to be paid by the HNRCA or by study funds. This information is provided to participants prior to their signing an informed consent form.

A participant may be dropped from the study should a reported adverse reaction to the study supplement be considered severe.

G. Subject Safety and Data and Safety Monitoring Plan

Classification and Reporting of Adverse Events and Unanticipated Problems for This Study

An **Unanticipated Problem** is defined as: An incident, experience, or outcome that meets all of the following criteria:

1. The nature, severity, or frequency is unexpected for the subject population or research activities as described in the current IRB approved protocol, supporting documents, and the ICF(s).
2. It is related or possibly related to participation in the research.
3. It suggests the research may place the subject or others at a greater risk of harm than was previously recognized.

An **Adverse Event (AE)** is defined as: Any untoward or unfavorable medical occurrence in a human subject, including any abnormal physical exam or laboratory finding, symptom, or disease, temporally associated with a subject’s participation in the research.

AEs are classified by three categories:

1. Severity: *Non-serious* or *Serious*
2. Relation to Participation in Research: *Related, Possibly Related, or Unrelated*

The classification of the potential relationship to the intervention will be determined based on the following scheme:

Definite	Temporal pattern and known or expected adverse event response pattern, confirmed by stopping the intervention and reappearance of adverse event on re-challenge.
Probable	Temporal pattern and known or expected adverse event response pattern, confirmed by stopping the intervention and which could not be explained by the participant’s clinical state.
Possible	Temporal pattern and known or expected adverse event response pattern, confirmed by stopping the intervention and which could have been produced by a number of other factors.
Unknown	Relationship for which no evaluation can be made.
Not Related	Adverse event for which sufficient information exists to indicate that the cause is unrelated to the study intervention.

3. Expectation: *Expected* or *Unexpected* (determination is based on the known risks associated with the study supplement and procedures, natural progression of an underlying illness, and health characteristics of the study population)
4. Location: *Internal* (occurring at the HNRCA) or *External* (occurring at a site that is not under the jurisdiction of the Tufts MC/TUHS IRB)

Further, a **Serious Adverse Event (SAE)** is an **AE** that meets the following criteria:

1. Results in death, or
2. Is life-threatening, or
3. Results in hospitalization or prolongation of existing hospitalization, or
4. Results in a persistent or significant disability/incapacitation, or
5. Results in congenital anomaly/birth defect, or
6. May jeopardize the subject's health and may require medical or surgical intervention to prevent one of the other outcomes listed above.

AEs are Unanticipated Problems only when they meet all three criteria in the definition of an unanticipated problem.

In the event of an Unanticipated Problem, or adverse event, staff will immediately notify the PI and study physician. Once notified, the PI, [name], will take immediate action to eliminate or minimize risk to enrolled subjects. The study physician, [name], will assess the severity of the unanticipated problem, and determine its relation to the study protocol. Each unanticipated problem will be reported, with all supporting documentation, according to the following IRB guidelines within 5 business days:

Information that does not fall under any of the categories does not require reporting to the IRB.

1. Harm experienced by a subject or other individual, which in the opinion of the investigator is **unexpected** and **related/possibly related** to the research procedures.
 - A. A harm is "**unexpected**" when its specificity and/or severity is **inconsistent** with risk information previously reviewed and approved by the IRB in terms of nature, severity, frequency, and characteristics of the study population.
 - B. A harm "**possibly related**" when there is a reasonable likelihood that the incident, experience, or outcome may have been caused by the procedures involved in the research.
- b. Information that indicates a new or increased risk, or a new safety issue. For example:
 - A. New information (e.g., an interim analysis, safety monitoring report, publication in the literature, sponsor report, or investigator finding) indicates an increase in the frequency or magnitude of a previously known risk, or

uncovers a new risk or greater risk of harm (including physical, psychological, economic, or social harm) than was previously known or recognized.

- B. An investigator brochure, package insert, or device labeling is revised to indicate an increase in the frequency or magnitude of a previously known risk, or describe a new risk
- C. Withdrawal, restriction, or modification of a marketed approval of a drug, device, or biologic used in a research protocol
- D. Complaint of a subject that indicates subjects or others might be at increased risk of harm or at risk of a new harm
- E. Any changes or new information adversely affecting the conduct of the research (that indicates a new or increased risk, or a new safety issue)
- b. Non-compliance with the federal regulations governing human research or with the requirements or determinations of the IRB, or an allegation of such non-compliance
- c. Audit, inspection, or inquiry by a federal agency and any resulting reports (e.g. FDA Form 483)
- d. Any site monitoring or other audit report finding that directly and materially affects subject safety or their willingness to continue participation
- e. Failure to follow the protocol that harmed a subject or placed subject at risk of harm (for example, missed study test or visit (or out of window) that could affect subject safety, enrollment of a subject who did not meet all eligibility criteria, failure to follow safety monitoring plan. These examples are intended as a guide and are not all-inclusive.)
- f. Breach of confidentiality
- g. Change to the protocol taken without prior IRB review to eliminate an apparent immediate hazard to a subject
- h. Incarceration of a subject in a study not approved by the IRB to involve prisoners
- i. Complaint of a subject that indicates that the rights, welfare, or safety of the subject have been adversely affected or a subject complaint that cannot be resolved by the research team
- j. Premature suspension or termination of the protocol by the sponsor, investigator, or institution
- k. State medical board actions against any member of the research team
- l. [Unanticipated adverse device effect](#) (any serious adverse effect on health or safety or any life-threatening problem or death caused by, or associated with, a device, if that effect, problem, or death was not previously identified in nature, severity, or degree of incidence in the investigational plan or application (including a supplementary plan or application), or any other unanticipated serious problem associated with a device that relates to the rights, safety, or welfare of subjects.)
- m. Information that, per the sponsor, requires prompt reporting to the IRB

Data and Safety Monitoring Plan:

As this study is low-risk, it does not have a Data and Safety Monitoring Board (DSMB). The PI, along with the IRB, will ensure that volunteer safety and data integrity are maintained through our Data and Safety Monitoring Plan. This Data and Safety Monitoring Plan (DSMP) outlines the PI's, [name], role as follows:

- [name] will regularly monitor potential risks and procedures in order to protect participants from risk.
- Will discuss any adverse events with the study physician on a weekly basis.
- Will report any adverse events associated with participation in the study protocol and file all required annual paperwork with the IRB.
- Will evaluate the progress of the study including periodic assessments of data quality and timeliness, recruitment, enrollment and retention, protocol violations, unanticipated events, volunteer risk vs. benefit, and anything else that may have an impact on the study outcome.
- Maintain vigilance of developments outside of the study that could affect participant's safety.
- Perform, at minimum, two reviews of the data per year to ensure safety and efficacy of the study.
- Responsibility for all procedures performed.
- Reviews all data as it may relate to volunteer safety. This includes factors like participant retention and reason for drop-out.
- Reporting all serious adverse events regardless of their relation to the study protocol.
- Provide the IRB with summaries of all adverse events.
- At the discretion of [name], the Co-I, [name], or [name], the study may be terminated at any time if the risks to study subjects are found to outweigh the potential benefits.

Additionally, no personal results will be communicated to study participants. However, participants will be informed of any necessary new findings developed during the course of this research study. Written results may be given directly, or mailed, to participants if they are still in the study, or mailed to them if they have completed their participation in the study.

H. Outcome

Our goal is to assess the safety and efficacy of EMIQ as it relates to body fat reduction. We predict that there will be no changes in health, and that there will be a significant difference between change in total body fat between the treatment and placebo groups.

I. Tissue Banking Considerations

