Version Date: 3/2/2018

Principal Investigator: [name]

Co-Investigator: [name]

Study Physician: [name]

Study Title: Body Fat Reducing Effect and Safety of Enzymatically Modified Isoquercitrin in Overweight and Obese Subjects

I. Aim and Hypotheses

Specific Aim 1: To compare the body fat reducing effect of 360mg/day enzymatically modified isoquercitrin (EMIQ) with that of a placebo.

Hypothesis 1: Compared to a placebo, participants receiving EMIQ supplementation will have a greater reduction in total body fat as evidenced by measures of whole body DXA scan, skinfold thickness, waist to hip circumference ratio, resting metabolic rate, plasma adiponectin levels, physical activity, and dietary intake.

Specific Aim 2: To determine the safety of long term intake of EMIQ.

Hypothesis 2: Long-term intake of EMIQ has no ill effect on participant health as evidenced by measures of heart, liver, kidney function, and psychological state.

II. Background and Rationale

Dietary quercetin is a natural bioactive polyphenol with potential health benefits and the capacity to prevent development of various diseases including those of the cardiovascular system, central nervous system and others [1-3]. It is widely distributed in various plant foods such as onions, broccoli, concord grapes, apples and more [4]. In plants, quercetin is present as conjugated with different forms of glucosides [5], which affect their bioavailability. The bioavailability of different forms of quercetin has been the subject of several investigations [6]. Enzymatically-modified isoquercitrin (EMIQ) is a mixture of quercetin monoglucoside and its α -oligoglucosides, which mainly consist of quercetin-3-O- β -glucoside (Q3G) and α -glucosyl derivatives with 1-7 of additional linear glucose moieties [7, 8]. Supplementing the diet of apoE-deficient mice with EMIQ increased quercetin levels and suppressed atherogenesis in this mouse model of human atherosclerosis[9]. In human trials, the bioavailability of EMIQ

has been shown to be 17-fold higher than quercetin aglycone [10]. After efficient absorption of EMIQ, quercetin is released, and it exerts its biological activity such as reducing body fat, improving cardiovascular health and reducing blood pressure.

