To calculate number of subjects needed per group and provide 80% power at $\alpha=0.05$ we used mean differences and standard deviation (EMIQ: 19 ± 24.62 and Placebo: 1 ± 12.87) of whole abdominal fat loss from an early published study conducted in Japan, where the Japanese volunteers consumed 275mg EMIQ per day for 12 weeks and showed a positive impact of EMIQ on reduction of fat depots. We plugged in data from that study into this formula $N=1+[16(xS^2/d^2)]$ to calculate sample size. Using this formula the number of subjects in each group were calculated to be $n=18$. However, we selected to use 25 subjects per group which increases power of study to $>85\%$. 25 subjects per group is a conservative sample size, which make us to expect a larger difference in the means with a higher dose of EMIQ intake.

The primary objective of this study is to demonstrate reduction of total body fat following 12 weeks of EMIQ intervention. Therefore, we will determine statistically if EMIQ is effective to reduce percent body weight, total abdominal fat, subcutaneous and visceral fat after 12 weeks of intervention compared to baseline values. We plan to compare the two group medians with the Mann-Whitney U test. After reviewing the data at the completion of the study, we can assume normality, then we will compare the two group means with parametric t-test.

C. Subject Characteristics

Inclusion Criteria:

- Male or female age 18-65 years.
- Premenopausal female with regular menstrual cycle or post-menopausal female with cessation of menstrual cycle for a minimum of 6 months.
- BMI in the range of 26.0-37.0_
- Beck Depression Inventory Score less than 20.
- Fluency in spoken or written English.
- Willingness to be randomized to take EMIQ or placebo.
- Must weigh at least 164lbs

Exclusion Criteria:

- Any major illness or condition that may interfere with study outcomes at the discretion of the study physician.
- Diabetes Type I & Type II, or use of any pharmacological treatment for diabetes.
- Use of medications that interfere with energy metabolism
- Receiving hormone therapy growth hormone, testosterone, or estrogen with the exception of hormone contraceptives.
- GI diseases, conditions or medications known to influence GI absorption including active peptic ulcer disease or inflammatory bowel disease such as

- ulcerative colitis, Crohn's disease, celiac disease, chronic diarrhea or constipation.
- Undergone gastric bypass or other bariatric weight loss procedure.

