## Statistical Analysis Plan

All subjects who completed the study were included in the analysis. Summary statistics were expressed in mean  $\pm$  S.D. for continuous variables, and counts (percentage %) for categorical variables. Differences between treatment groups were tested using Student's *t*-test. Two-sample Wilcoxon test is used when variables appear to violate distributional assumptions. Model assumptions were assessed within an ANCOVA model predicting 12 week outcome, adjusting for baseline. Fisher's exact test or chi-square test was performed for categorical variables. An  $\alpha$  level of  $p < 0.05$  was considered statistically significant. Statistical analysis was conducted in R 3.4 (R Core Team 2017, Vienna Austria).

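### Hypothesis 2 asserts no ill effect, but the only planned inference is tests for a difference at p < 0.05 in completers, and non-significance with 25 per arm would leave moderate harm open

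*Protocol*

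**What the plan says.** Safety is the second of two specific aims. Protocol section I, Hypothesis 2, reads: "Long-term intake of EMIQ has no ill effect on participant health as evidenced by measures of heart, liver, kidney function, and psychological state". Section III.H (Outcome) repeats the expectation: "We predict that there will be no changes in health".

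The SAP does not treat safety variables separately. For continuous variables, "Differences between treatment groups were tested using Student's *t*-test", and "Two-sample Wilcoxon test is used when variables appear to violate distributional assumptions". For the rest, "Fisher's exact test or chi-square test was performed for categorical variables". The threshold is p < 0.05. Means with SDs and counts with percentages are the planned summaries. An ANCOVA adjusting for baseline is mentioned, but only as the setting in which assumptions are checked. The analysis set is subjects who completed the study.

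The sample size in Protocol section III.B rests on efficacy alone ("EMIQ: 19 ± 24.62 and Placebo: 1 ± 12.87) of whole abdominal fat loss"): 18 per group by formula, raised to 25. Neither document gives a safety margin, an equivalence or non-inferiority test, a confidence interval for a safety difference, or a power statement for safety.

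**The concern.** A test for a difference can contradict a claim of no effect, but it cannot establish one. Under this plan, the only inferential result consistent with Hypothesis 2 is failure to reject. That is a likely result in a small trial whether or not there is harm, and no other criterion for the hypothesis is written. A report that follows the SAP could therefore list non-significant p-values for liver, kidney, EKG and Beck results and offer them as support for safety.

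The analysis set adds to this. The withdrawal criteria in section III.C include negative health effects as judged by the study physician. Subjects withdrawn on that ground are not completers, so the subjects most informative for Hypothesis 2 can fall outside the comparison.

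**Working it through.** **The plan's own figure.** Section III.B uses N = 1 + 16·S²/d², with d = 19 − 1 = 18. Taking S as the mean of the two SDs, (24.62 + 12.87)/2 = 18.745, gives N = 1 + 16 × 351.375/324 = 18.35, which matches the stated 18. At 25 per group, t-based power is 91% with that S, or 89% with S² as the mean variance (S = 19.64). Both agree with the stated figure of more than 85%. The efficacy sizing is not the defect; it simply says nothing about safety.

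**Inputs for safety.** n = 25 per arm (50 completers, 1:1, section III.B) and α = 0.05 (SAP). The SAP does not state sidedness, so two-sided is assumed. The documents give no safety effect sizes, margins or event rates, so every such value below is an assumption, shown as a range.

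**Continuous measures.** The standard error of a mean difference, in SD units, is √(2/25) = 0.283.

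- The 95% CI half-width is t(0.975, 48) × 0.283 = 2.011 × 0.283 = 0.57 SD.
- Power to detect a shift δ uses the noncentral t with 48 df and noncentrality δ/0.283.
- Power to exclude a shift m when the true difference is zero (one-sided 0.025, normal approximation) is Φ(m/0.283 − 1.96). The number per arm for 80% power is 2(1.96 + 0.842)²/m².

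| Assumed shift | Power to detect it | Power to exclude it | n per arm to exclude it with 80% power |
|---|---|---|---|
| 0.2 SD | 11% | 11% | 393 |
| 0.3 SD | 18% | 18% | 175 |
| 0.5 SD | 41% | 42% | 63 |
| 0.8 SD | 79% | 81% | 25 |

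A true harmful shift of 0.5 SD would be non-significant in about 59% of such trials (100% − 41%). Detection with 80% power needs about 0.81 SD.

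**Events.**

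- Split of 5/25 against 0/25: the one-sided Fisher probability is C(25,5)/C(50,5) = 53,130/2,118,760 = 0.0251. The two-sided p is twice that, 0.0502, so it is not significant.
- Exact Fisher power: 7% for 15% vs 5%, 20% for 20% vs 5%, 23% for 20% vs 4%, and 38% for 20% vs 0%.
- No events among 25: the upper limit is 1 − 0.025^(1/25) = 13.7% for a two-sided 95% interval, or 1 − 0.05^(1/25) = 11.3% one-sided.
- An event with a true rate of 5% would be missed altogether in 25 subjects with probability 0.95²⁵ = 28%.

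**Sensitivity.**

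- If baseline-adjusted differences were reported and the baseline correlation were 0.7 (assumed), the half-width would shrink to 0.57 × √(1 − 0.49) = 0.41 SD.
- If events were counted in all 64 enrolled (32 per arm), no events would leave 1 − 0.025^(1/32) = 10.9% two-sided, or 8.9% one-sided.

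Both are better than the planned comparison, and neither gets close to showing no ill effect.

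**The case against.** Three stronger readings are tempting, and the documents support none of them.

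- *The plan will declare safety when p > 0.05.* No passage says so. Hypothesis 2 is a hypothesis, section III.H a prediction, and the SAP a list of tests. What stands is that no other criterion is written, so this reading is left open.
- *Nothing else in the plan bears on safety.* This is not so. The SAP's means, SDs and counts would let a reader compute unadjusted intervals. The protocol plans liver and kidney tests at visits 3 and 4, EKGs at visits 2 and 3, the Beck inventory at screening and visit 5, adverse-event grading, physician review and reporting to the IRB (sections III.E to III.G). These protect individuals and yield useful data, but none is tied to a rule for judging Hypothesis 2.
- *The trial cannot show safety at all.* That depends on a margin, and none is given. With 25 per arm the trial has about 81% power to exclude a 0.8 SD shift. The shortfall is at 0.5 SD and below.

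It can also be said that body fat reduction is the stated primary objective, that the product has GRAS status, and that small efficacy trials seldom have precise safety data. All of that is true, and it argues against asking for more subjects. It does not make a difference test suitable for a claim of no effect.

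**Conclusion.** The concern holds in a limited form. On one of the two aims, the planned inference cannot support the hypothesis as worded. The size of the gap depends on the assumed harm: with 25 completers per arm and two-sided α = 0.05, a shift of about 0.8 SD can be detected or excluded with roughly 80% power, while a shift of 0.5 SD is missed more often than not. For events, a 5 to 0 split would pass as non-significant. The effect sizes and event rates are assumptions, the main figures are for unadjusted comparisons, and the judgement rests on the SAP text available. The primary efficacy analysis is unaffected. This is an inexpensive correction that should be made, not a flaw in the design.

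**What to change.** In the SAP:

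1. Report each safety laboratory value, vital sign, EKG measure and Beck score as a between-arm difference with a 95% confidence interval, adjusted for baseline where a baseline exists.
2. Report adverse-event proportions by arm with exact 95% confidence intervals in all subjects who took any study capsules (EMIQ or placebo), not in completers only.
3. State that p > 0.05 is not evidence of safety.

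In the protocol, reword Hypothesis 2, and the matching prediction in section III.H, so that the conclusion is the size of effect the confidence interval excludes.

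No new subjects, visits or measurements are needed. The cost is a few more table columns, revised wording in both documents and a more modest safety claim.
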